**Figure 2 Study Schema**

DLBCL = diffuse large B-cell lymphoma; EOI = end of induction; FL = follicular lymphoma; RP2D = recommended Phase II dose.

Approximately 140 patients with R/R FL and DLBCL are expected to be enrolled in this study at approximately 25 investigational sites worldwide.

All patients will be closely monitored for adverse events throughout the study and for at least 90 days after the last dose of study treatment (see Section 5.3.1). Adverse events will be graded according to the National Cancer Institute Common Toxicity Criteria, Version 4.0 (NCI CTCAE v4.0). An internal monitoring committee (IMC) will be established to monitor patient safety throughout the study (see Section 3.1.4).

To characterize the PK properties of obinutuzumab or rituximab, idasanutlin, and venetoclax when given in combination, blood samples will be taken at various timepoints before and during study treatment administration (see [Appendix 3](#)).

Response will be determined by the IRC (see Section [3.1.5](#)) and the investigator using the modified Lugano 2014 criteria (see [Appendix 4](#)). The primary efficacy endpoint will be based on IRC assessment of response. Refer to Section [4.5.5](#) for details on tumor assessments.

The schedules of activities are provided in [Appendix 1](#) and [Appendix 2](#); the schedule for PK and biosample assessments is presented in [Appendix 3](#).

*The Sponsor may decide to delay, suspend, or terminate enrollment within a given arm. Experimental arms with insufficient clinical activity or unacceptable toxicity will not undergo expansion. New experimental arms may be added during the study by amending the protocol.*

### **3.1.2 Dose-Escalation Phase**

The purpose of the dose-escalation phase is to identify the RP2Ds and regimen for idasanutlin and venetoclax when combined with a fixed dose of obinutuzumab in patients with R/R FL and the RP2D for idasanutlin and venetoclax when combined with 375 mg/m^2 of rituximab in patients with R/R DLBCL. The RP2Ds will be based on the MTDs of idasanutlin and venetoclax when combined with a fixed dose of obinutuzumab or with 375 mg/m^2 of rituximab, but will also take into account all safety data during treatment. There could be two different RP2Ds and/or regimens dependent on the combination of idasanutlin, venetoclax plus obinutuzumab or idasanutlin, and venetoclax plus rituximab.

A minimum of 9 patients and a maximum of 60 patients will be enrolled during the dose-escalation phase. Cohorts of 3–6 patients each will be treated at escalating doses of idasanutlin and venetoclax in accordance with the treatment regimens and dose-escalation rules described in Section [3.1.2.2](#).

A Bayesian mCRM (see Section [3.1.2.3](#)) is planned to guide the dose-escalation phase to determine the MTD that achieves the efficacious exposure observed. The principle underlying this trial design is the assessment of the dose-toxicity relationship in a safe and efficient manner, allowing for enrollment of patients at subsequent dose levels and/or defining the MTD with robust data, including data for patients from Study BH29812 (obinutuzumab or rituximab in combination with idasanutlin), when available.

Patients will be closely monitored for adverse events during the DLT assessment window, defined as the first two treatment cycles. Adverse events meeting the criteria for

DLT, as defined in Section 3.1.2.1, will be reported to the Sponsor within 24 hours (see Section 5.4.2).

Patients experiencing a DLT during the DLT window (first two cycles of treatment) will permanently discontinue study treatment.

Patients who discontinue from the study prior to completing the DLT assessment window for reasons other than a DLT will be considered non-evaluable for dose-escalation decisions and MTD assessments and will be replaced by an additional patient at that same dose level. Patients who miss more than one dose of obinutuzumab or rituximab, idasanutlin, or venetoclax during the DLT assessment window for reasons other than a DLT will also be considered non-evaluable and will be replaced.

Additional cohorts may be added following the Sponsor's decision to explore idasanutlin's therapeutic advantage as consolidation or maintenance treatment. The decision for opening such cohorts will be based on long-term safety and tolerability data.

### 3.1.2.1 Definition of Dose-Limiting Toxicity

In this study, a DLT is defined as at least one of the following events occurring during the first two cycles of treatment and assessed by the investigator as clearly not related to the patient's underlying disease:

- Any Grade 5 adverse event unless unequivocally due to the underlying malignancy or extraneous causes
- Adverse event of any grade that leads to a delay of more than 14 days in the start of the next treatment cycle
- Hematologic adverse events that meet any of the following criteria:
  - Grade 3 or 4 neutropenia in the presence of sustained fever of  $>38^{\circ}\text{C}$  (lasting for  $>5$  days) or a documented infection
  - Grade 4 neutropenia lasting for  $>7$  days *despite adequate supportive care measures. G-CSF may be used to treat Grade  $\geq 3$  neutropenia but should not be used as prophylaxis in the DLT period.*
  - Grade 3 or 4 thrombocytopenia if associated with grade  $\geq 3$  bleeding
  - Grade 4 thrombocytopenia lasting for  $>7$  days
- Grade 3 or 4 non-hematologic adverse event, with the following exceptions:
  - Grade 3 or 4 IRRs
    - Note that IRRs are not dose-dependent events. They may occur even after a small amount of drug has been administered.
  - Grade 3 laboratory TLS without manifestations of clinical TLS (see [Appendix 5](#) for the Howard-based criteria for clinical and laboratory TLS)
  - Grade 3 AST or ALT increase lasting  $<7$  days
  - Grade 3 diarrhea that responds to adequate therapy within 48 hours

- Grade 3 nausea or vomiting that occurs in the absence of premedication and responds to adequate therapy within 72 hours
- Grade  $\leq 3$  fatigue, asthenia, anorexia, or constipation that resolves to Grade  $\leq 2$  in  $\leq 7$  days
- Any increase in hepatic transaminase  $> 3 \times$  baseline AND an increase in direct bilirubin  $> 2 \times$  ULN, WITHOUT any findings of cholestasis or jaundice or signs of hepatic dysfunction AND in the absence of other contributory factors (e.g., worsening of metastatic disease or concomitant exposure to known hepatotoxic agent or of a documented infectious etiology) is suggestive of potential drug induced liver injury (DILI) (according to Hy's Law) and will be considered a DLT.

Other toxicities that are considered clinically relevant and related to study treatment as determined by the investigator and the Medical Monitor may also be considered DLTs.

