### **Investigational Medicinal Products**

#### **Test Product (Investigational Drug)**

Study treatment will be administered in 28-day cycles.

Obinutuzumab will be administered by intravenous infusion at an absolute (flat) dose of 1000 mg on Days 1, 8, and 15 of the first cycle and on Day 1 of each subsequent cycle during induction treatment, and on Day 1 of every other month (i.e., every 2 months) for 24 months during maintenance treatment (eligible patients with FL only) or for 6 months during consolidation treatment (eligible patients with DLBCL only).

Rituximab will be administered by intravenous infusion at a dose of 375 mg/m^2 on Day 1 of Cycles 1–6 during induction treatment and on Day 1 of every other month (i.e., every 2 months) for 6 months during consolidation treatment (eligible patients with DLBCL only).

Idasanutlin tablets will be taken once daily by mouth, approximately 15 minutes after eating a meal and with water, on Days 1–5 of Cycles 1–6 (or Cycles 2–6 for the bridging cohorts in FL patients and in the expansion phase if this regimen is chosen), followed by 6 months of post-induction treatment. The starting dose will be 100 mg during the dose-escalation phase. The RP2D with the selected regimen will be administered during the expansion phase. The dose and regimen for post-induction treatment will be determined by the Sponsor after review of all relevant data.

Each once-daily dose of venetoclax will be taken orally with approximately 240 mL of water within approximately 30 minutes after the completion of breakfast or the first meal of the day. For Cycles 1–6 (induction; or Cycles 2–6 for the bridging cohorts in FL patients and in the expansion phase if this regimen is chosen) and for 6 months thereafter (post-induction), venetoclax will be given once-daily on Days 1–5 or Days 1–10 depending on tolerability. The selection of the venetoclax dose schedule will be determined according to the dose-escalation plan. The starting dose will be 200 mg during the dose-escalation phase. The RP2D with the selected regimen will be administered during the expansion phase. The dose and regimen for post-induction treatment will be determined by the Sponsor after review of all relevant data.

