### **3.1.2.2 Treatment Regimens and Dose-Escalation Rules Patients with FL and DLBCL until the Bridging cohorts**

[figure not shown]
During this first dose-escalation phase, patients will be enrolled according to the schema in [Figure 3](#). Three patients will initially be enrolled in each cohort, and up to 3 additional patients can be enrolled in a cohort at the Sponsor's discretion. The first patient in each cohort will be observed for safety for 1 week after Cycle 1 Day 1 before additional patients are enrolled in the same cohort. A minimum of 3 patients enrolled in a cohort must complete at least the first two cycles (i.e., the DLT assessment window, until Cycle 2, Day 28) before enrollment commences in the next cohort(s). Intra-patient dose escalation is not permitted in this study.

Enrollment will begin in a safety cohort in which patients will be treated at starting doses of 100 mg QD on Days 1–5 of each cycle for idasanutlin and 200 mg QD on Days 1–5 of each cycle for venetoclax, given in combination with obinutuzumab at the standard dose on Days 1, 8, and 15 of Cycle 1 and Day 1 of subsequent cycles (see [Figure 3](#) for details on treatment regimens). If treatment in the safety cohort is well tolerated, treatment will be initiated in Cohort 1 at the same doses as the safety cohort, except that patients will receive venetoclax on Days 1–10 of each cycle (see [Figure 3](#)). This regimen is referred to as Regimen A.

If the initial treatment regimen is not tolerated in the safety cohort, any subsequent cohorts will receive venetoclax on Days 1–5 of each cycle.

If safety and tolerability allow, the next two cohorts (Cohorts 2 and 3) will be enrolled concurrently. Patients in Cohort 2 will receive an escalated dose of venetoclax, while patients in Cohort 3 will receive an escalated dose of idasanutlin. Thus, only one drug will be escalated within each of the concurrent cohorts. If safety and tolerability allow, patients in Cohort 4 will receive both venetoclax and idasanutlin at the escalated doses given in the previous two cohorts (see [Figure 3](#)).

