### **Combination of Obinutuzumab, Idasanutlin, and Venetoclax in Patients with FL in the Bridging Cohorts**

Following the identification of the MTDs for idasanutlin and venetoclax in combination with obinutuzumab in Regimen A, *or following Sponsor decision based on clinical judgment*, a bridging cohort of patients with FL will be opened to *repeat the last dose tested* in a different regimen. Obinutuzumab will be given alone in Cycle 1 and in combination with idasanutlin and venetoclax from Cycle 2 to 6 (see [Figure 4](#) and [Table 1](#)). This regimen is referred to as Regimen B.

If safety and tolerability allow, idasanutlin and venetoclax dose escalation may be explored with Regimen B in patients with FL until identification of new MTDs (see [Figure 4](#)).

After the last patient in each cohort has completed the two-cycle DLT observation period, the Sponsor, in consultation with the investigators, will evaluate the next dose recommended according to the mCRM (see [Section 3.1.2.3](#)) and agree on doses for the subsequent cohort(s), taking into account relevant demographic, adverse event, laboratory, dose administration, and PK (if available) data. At each dose-escalation step, the dose may be escalated or de-escalated, or an additional cohort at the same dose level may be enrolled.

[figure not shown]
On the basis of review of real-time safety data from this study and all available data from Study BH29812, dose escalation may be halted or modified by the Sponsor as deemed appropriate.

Although the DLT assessment window is defined as the first two treatment cycles, cumulative toxicities occurring beyond the first two cycles may be considered when determining the MTDs for idasanutlin or venetoclax.

Multiple MTDs may be identified, and the most appropriate RP2Ds will be chosen on the basis of safety, PK, and PD data. At the end of dose–escalation phase, RP2Ds (one for idasanutlin and one for venetoclax) in combination with obinutuzumab and one regimen will be decided for patients with FL. RP2Ds (one for idasanutlin and one for venetoclax) in combination with rituximab will be decided for patients with DLBCL. The RP2Ds of idasanutlin and venetoclax, as well as the treatment regimens for patients with FL and DLBCL, may be different.

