#### **5.1.8 Management of Patients Who Experience Specific Adverse Events**

Patients should be assessed clinically before each study treatment administration.

Guidelines for management of toxicities are based on laboratory values obtained within 48 hours prior to Day 1 of each scheduled drug administration or within 24 hours prior to Days 8 and 15 of Cycle 1. Dosing will occur only if a patient's clinical assessment and laboratory test values are acceptable.

During induction, study treatment may be delayed for toxicity for a maximum of 21 days. If study treatment is delayed for more than 21 days, obinutuzumab or rituximab, idasanutlin, and venetoclax treatment will be permanently discontinued (see [Table 18](#)).

There will be no dose reductions of obinutuzumab or rituximab. Treatment delays apply to all toxicities described below; dose modifications apply only to toxicities that are considered to be related to either idasanutlin and/or venetoclax. The dose of idasanutlin may be reduced as outlined in [Table 15](#). The dose of venetoclax may also be reduced.

In parallel cohorts, in which one drug only is escalated, the dose of that drug can be reduced only once per treatment cycle. In diagonal cohorts, in which the doses of both drugs have been escalated, the dose of both drugs will be reduced once per treatment cycle. There will be no more than one dose reduction per treatment cycle. If the doses of idasanutlin and venetoclax are reduced, re-escalation is not permitted.

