#### **5.4.2.2 Events That Occur after Study Treatment Initiation**

After initiation of study treatment, all adverse events will be reported until 90 days after the last dose of study treatment. DLTs will be reported during the DLT assessment window. Investigators should record all case details that can be gathered immediately (i.e., within 24 hours after learning of the event) on the Adverse Event eCRF and submit the report via the electronic data capture (EDC) system. A report will be generated and sent to Roche Safety Risk Management by the EDC system.

In the event that the EDC system is unavailable, the Serious Adverse Event/Adverse Event of Special Interest Reporting Form provided to investigators should be completed and submitted to the Sponsor or its designee immediately (i.e., no more than 24 hours after learning of the event), either by faxing or by scanning and emailing the form using the fax number or email address provided to investigators. Once the EDC system is available, all information will need to be entered and submitted via the EDC system.

Instructions for reporting serious adverse events that occur >90 days after the last dose of study treatment are provided in Section 5.6.

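### A Cycle 3 delay of more than 14 days is a DLT criterion, but the DLT window, the next cohort and the dose decision can all close at Cycle 2 Day 28, about 15 days before that criterion can be settled

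*Protocol*

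**What the plan says.** Protocol Section 3.1.2.1 limits DLTs to "events occurring during the first two cycles of treatment and assessed by the investigator as clearly not related to the patient's underlying disease". One criterion is "Adverse event of any grade that leads to a delay of more than 14 days in the start of the next treatment cycle".

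Section 3.1.2.2 sets the gate to the next cohort. At least three patients must "complete at least the first two cycles (i.e., the DLT assessment window, until Cycle 2, Day 28) before enrollment commences in the next cohort(s"). The dose evaluation by the sponsor and investigators comes later in the same section: "After the last patient in each cohort has completed the two-cycle DLT observation period". That paragraph sits under the FL bridging-cohort heading but reads as a general rule.

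Section 5.4.2.2 adds: "DLTs will be reported during the DLT assessment window". Section 5.1.8 allows for long delays: during induction, "study treatment may be delayed for toxicity for a maximum of 21 days". Neither document says how a Cycle 3 delay that is still pending at Cycle 2 Day 28 is to be classified.

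**The concern.** The delay criterion looks forward from the cycle in which the event occurs. For a Cycle 1 event it concerns the start of Cycle 2 and resolves inside the window. For a Cycle 2 event it concerns the start of Cycle 3, which is not due until the day after the window closes. At the earliest time the protocol permits a decision, the criterion cannot be assessed for any Cycle 2 event.

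A patient whose Cycle 3 will turn out to be more than 14 days late can then enter the modified continual reassessment model (mCRM) as a non-event. The error runs one way: an open criterion can hide a DLT but cannot create one, so it favours escalation. At stake is whether new patients are allocated to a combination that the overdose rule would have excluded had the pending outcome been known.

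**Working it through.** **1. Calendar.** Cycle length is 28 days (Synopsis: "Study treatment will be administered in 28-day cycles"). With no earlier delay:
- Cycle 2 Day 28 = 2 × 28 = day 56, the protocol's own gate.
- Planned Cycle 3 Day 1 = day 57.
- A start on day 57 + 14 = day 71 is exactly 14 days late and does not count. The first start that counts is day 72, so the criterion is settled at the end of day 71.
- Gap = 71 − 56 = 15 days.

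For a Cycle 2 delay, planned Day 1 is day 29 and the criterion is settled at the end of day 29 + 14 = day 43, inside the window. Only Cycle 3 delays are affected.

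**2. Which events are exposed.** Section 3.1.2.1 already captures Grade 4 neutropenia or thrombocytopenia lasting more than 7 days, cytopenia with sustained fever, infection or severe bleeding, and most Grade 3–4 non-hematologic events. What remains is DLT-only-through-delay, for example:
- persisting uncomplicated Grade 3 cytopenia. Table 16 withholds treatment for it and provides for recovery 15–21 days late.
- Grade 2 non-hematologic toxicity, for which Table 18 can also hold dosing.

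In Regimen B the triplet starts in Cycle 2 (Section 3.1.2.2, Table 1). The first delay that can reflect the triplet is therefore a Cycle 3 delay, which always falls after the window.

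**3. How often.** The documents give no rate. Assume a per-patient probability p that a Cycle 3 delay is the only DLT. The chance of at least one in a cohort of n is 1 − (1 − p)^n, for cohorts of 3 to 6 (Section 3.1.2).

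| p (assumed) | n = 3 | n = 6 |
|---|---|---|
| 1% | 3.0% | 5.9% |
| 2% | 5.9% | 11.4% |
| 5% | 14.3% | 26.5% |
| 10% | 27.1% | 46.9% |

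**4. Effect on the model if one such DLT is not counted.** Inputs from Section 3.1.2.3: logit p = α₁ + β₁ log(idasanutlin/200); logit q = α₂ + β₂ log(venetoclax/400); π⁰ = p + q − pq; odds(π) = odds(π⁰) × exp(γ × product of the normalized doses); the printed bivariate normal priors; log γ ~ N(0.4, 1.0). As a check, exp(0.916) = 2.50 and exp(1.685) = 5.39 match the slopes 2.5 and 5.4 in Appendix 6, Table 1. The posterior comes from 1,000,000 prior draws weighted by the binomial likelihood. A combination is allowed if P(DLT rate >33%) is below 0.35. Doses are idasanutlin/venetoclax in mg.

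Data: 0/6 at 100/200, 0/3 at 100/400, 0/3 at 200/200, then 0/3 or 1/3 at 200/400.

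| Candidate | 0/3 counted | 1/3 counted |
|---|---|---|
| 250/400 | 0.29 | 0.61 |
| 200/500 | 0.33 | 0.63 |

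The same reversal appears at the first step, with only three patients at the starting 100/200.

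| Candidate | 0/3 counted | 1/3 counted |
|---|---|---|
| 200/200 | 0.336 | 0.752 |
| 100/400 | 0.141 | 0.403 |

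All four candidates move from allowed to not allowed. With 1/3 counted, 200/400 itself stays allowed (0.31), so the model would still permit that combination but neither step above it.

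**The case against.** **Day 28 is a floor.** The cohort rule requires at least two cycles, and the dose evaluation comes after the last patient completes them, on no fixed day. A reader might infer that the protocol requires the model to be updated on Day 28. It does not. It permits a decision then, and nothing makes the decision wait.

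**Safeguards exist.** Grade ≥3 neutropenia and thrombocytopenia are reportable within 24 hours (Sections 5.2.3 and 5.4), and hematology is drawn before each cycle (Appendices 1 and 2). Dose decisions take adverse event, laboratory and dosing data into account, and real-time review may halt escalation (Section 3.1.2.2). Clinical judgment takes precedence over the model (Section 3.1.2.3), and other relevant toxicities may be classed as DLTs (Section 3.1.2.1). An unresolved severe cytopenia would normally be visible. This stands and lowers the risk, but whether any of it leads to a wait or a reclassification is discretionary.

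**Late is not lost.** A reader might infer that these DLTs are dropped for good and bias the final MTD. The documents do not support that. The qualifying event occurs in Cycle 2 and remains a DLT by definition. Adverse events are reported until 90 days after the last dose, and the model is updated with DLTs from all tested cohorts (Appendix 6). Later cumulative toxicity may also inform the MTD.

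**Prolonged thrombocytopenia is not the example.** The 55-day Grade 4 case in Section 1.3.2 might be taken to show the gap. It would already be a DLT under the more-than-7-days criterion, so it does not.

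**Other readings of the window.** One could hold that only a Cycle 2 delay counts, because the delay itself must fall in the window. Nothing says so, and the criterion could then never reflect the triplet in Regimen B. SAP Section 2.3.5 ends a cycle when the next begins, which would keep a Cycle 3 delay inside Cycle 2. That is a reporting rule and conflicts with the protocol's explicit Cycle 2 Day 28.

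**Conclusion.** The concern holds in a limited form. One of the protocol's DLT criteria cannot be assessed for Cycle 2 events at the point where the window closes and the next cohort and dose decision are permitted. The gap is 15 days when there has been no earlier delay. It exposes only events that are DLTs through delay alone, and it matters most in Regimen B. The consequence is a possible premature escalation step, not a permanent omission.

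The model figures show that one uncounted DLT can reverse an overdose-control decision. They are conditional on such a DLT having occurred, and any single missed DLT in a cohort of three would act the same way. They use only the printed priors and no DLT data from Study BH29812, which may be added. The doses above the start are illustrative, since Table 1 leaves them to be determined. The frequency range of 1% to 10% per patient is an assumption.

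**What to change.** Reconcile Protocol Sections 3.1.2.1, 3.1.2.2 and 5.4.2.2. Enter a patient in the mCRM as DLT-free, and count that patient towards the minimum of three, only when every DLT criterion can be assessed. That is the case when:
- Cycle 3 has started;
- the patient has left for a reason other than toxicity, handled under the existing evaluability rule in Section 3.1.2; or
- the delay criterion has been settled.

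Extend the DLT reporting period to match, and state that the cycle-end definition in SAP Section 2.3.5 does not define the DLT window.

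Cost: a patient who starts Cycle 3 on schedule is settled on day 57, one day after the present gate. Where Cycle 3 has not started on schedule, the wait is up to about 15 days after Cycle 2 Day 28. No additional patients or assessments are needed.

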#### **4.6.2 Study Treatment Discontinuation**

Study treatment should be permanently discontinued in patients who experience any of the following:

- A DLT during the DLT window in patients enrolled in the dose-escalation phase
- Anaphylaxis, acute respiratory distress, or Grade 4 IRR
  - If a Grade 3 IRR is recurrent during the second and subsequent cycles, study treatment may be discontinued at the discretion of the investigator, following an individual benefit–risk assessment.
- Any adverse event that leads to a delay of more than 21 days in the start of the next treatment cycle

- Any hematologic adverse event that meets criteria for permanent discontinuation according to the guidelines provided in Section 5.1.8
- Hy's Law cases
- Grade  $\geq 3$  non-hematologic adverse event that has a reasonable possibility of being related to study treatment and either is life threatening or does not resolve to Grade  $< 2$  within 21 days
- Disease progression
- Pregnancy

In case of toxicity solely attributable to one drug of the combination requiring discontinuation, the other study drugs may be continued for patients experiencing clinical benefit as determined by the investigator after discussion with the Medical Monitor.

The primary reason for study treatment discontinuation should be documented on the appropriate eCRF.

Patients who discontinue study treatment will not be replaced, except as outlined below:

- During the dose-escalation phase, patients who discontinue study treatment prior to completing the DLT assessment window for reasons other than a DLT will be replaced by an additional patient at that same dose level.
- Patients who discontinue before having received at least one dose of each component of the combination will be replaced.

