### **5.2.3 Adverse Events of Special Interest (Immediately Reportable to the Sponsor)**

Adverse events of special interest are required to be reported by the investigator to the Sponsor immediately (i.e., no more than 24 hours after learning of the event; see Section 5.4.2 for reporting instructions). Adverse events of special interest for this study include the following:

- Cases of potential drug-induced liver injury that include an elevated ALT or AST in combination with either an elevated bilirubin or clinical jaundice, as defined by Hy's Law (see Section 5.3.5.7)
- Suspected transmission of an infectious agent by the study treatment, as defined below

Any organism, virus, or infectious particle (e.g., prion protein transmitting transmissible spongiform encephalopathy), pathogenic or non-pathogenic, is considered an infectious agent. A transmission of an infectious agent may be suspected from clinical symptoms or laboratory findings that indicate an infection in a patient exposed to a medicinal product. This term applies only when a contamination of any of the study treatment components is suspected.

- TLS of any grade, irrespective of causality
- Grade  $\geq 3$  neutropenia, including febrile neutropenia
- Grade  $\geq 3$  thrombocytopenia or Grade  $\geq 2$  thrombocytopenia if associated with hemorrhage or bleeding)
- Grade 2 diarrhea
- Grade  $\geq 2$  *C. difficile* infection
- Second malignancies

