#### **5.3.5.7 Abnormal Liver Function Tests**

The finding of an elevated ALT or AST ( $> 3 \times$  baseline value) in combination with either an elevated total bilirubin ( $> 2 \times$  ULN) or clinical jaundice in the absence of cholestasis or other causes of hyperbilirubinemia is considered to be an indicator of severe liver injury (as defined by Hy's Law). Therefore, investigators must report as an adverse event the occurrence of either of the following:

- Treatment-emergent ALT or AST  $> 3 \times$  baseline value in combination with total bilirubin  $> 2 \times$  ULN (of which  $\geq 35\%$  is direct bilirubin)
- Treatment-emergent ALT or AST  $> 3 \times$  baseline value in combination with clinical jaundice

The most appropriate diagnosis or (if a diagnosis cannot be established) the abnormal laboratory values should be recorded on the Adverse Event eCRF (see Section 5.3.5.2) and reported to the Sponsor immediately (i.e., no more than 24 hours after learning of the event), either as a serious adverse event or an adverse event of special interest (see Section 5.4.2).

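### The liver-specific DLT criterion cites Hy's Law but excludes patients with jaundice, so a qualifying case can go uncounted in the dose-escalation model

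*Protocol*

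**What the plan says.** Protocol Section 3.1.2.1 lists the events that make a DLT in Cycles 1 and 2. The liver-specific bullet requires a transaminase above 3 times baseline with direct bilirubin above 2 times ULN, and applies only "WITHOUT any findings of cholestasis or jaundice or signs of hepatic dysfunction AND in the absence of other contributory factors". Such a case "is suggestive of potential drug induced liver injury (DILI) (according to Hy's Law) and will be considered a DLT".

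Two other sections define Hy's Law differently. Section 5.2.3 lists as an event of special interest "an elevated ALT or AST in combination with either an elevated bilirubin or clinical jaundice, as defined by Hy's Law". Section 5.3.5.7 requires reporting of a treatment-emergent ALT or AST above 3 times baseline with total bilirubin above 2 times ULN (at least 35% of it direct). It also requires reporting of the same transaminase rise at more than 3 times "baseline value in combination with clinical jaundice". It sets aside only cholestasis and other causes of hyperbilirubinemia.

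Section 4.6.2 lists Hy's Law cases as a reason for permanent discontinuation, as an item separate from a DLT. It adds that in dose escalation "patients who discontinue study treatment prior to completing the DLT assessment window for reasons other than a DLT will be replaced". Under Section 3.1.2, a patient who leaves the study before the window ends for a non-DLT reason "will be considered non-evaluable for dose-escalation decisions and MTD assessments". The same section treats as non-evaluable, and replaces, a patient who misses more than one dose of a study drug in the window for a non-DLT reason.

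**The concern.** Jaundice qualifies a case in Section 5 and disqualifies it in the DLT rule, under the same name. Read literally, the liver bullet counts the milder presentation and drops the clinically worse one. Excluding cholestasis agrees with Section 5.3.5.7; excluding jaundice and hepatic dysfunction does not.

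The mCRM takes DLT counts as its only outcome data, and Section 3.1.2.3 bars any dose combination with 35% or more posterior probability that the DLT rate exceeds 33%. If a patient is taken off treatment in the window for a Hy's Law event and is then replaced, the model that sets the next dose sees one DLT too few.

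**Working it through.** **Which patients fall through.** Take ALT or AST above 3 times baseline with clinical jaundice, and go through the DLT routes in Section 3.1.2.1:

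- *Grade 5*: not met.
- *Grade 3 or 4 non-hematologic event*: not met if every event is below Grade 3. Table 18 labels a transaminase level of 5 times ULN as Grade 2, so a rise above 3 times baseline can stay below Grade 3. A Grade 3 AST or ALT rise lasting under 7 days is exempt.
- *Liver bullet*: excluded because jaundice is present.
- *Delay rule*, "Adverse event of any grade that leads to a delay of more than 14 days in the start of the next treatment cycle": the text does not say whether a patient with no next cycle meets it.
- *Investigator and Medical Monitor discretion*: permitted, not required.

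Section 4.6.2 still stops treatment. If neither of the last two routes is used, the stop is not for a DLT and Section 4.6.2 replaces the patient. If more than one dose is missed, Section 3.1.2 also makes the patient non-evaluable.

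**Effect on the model.** The plan gives no figure for this point, so there is none to reproduce. The following is an illustration from the model and priors in Section 3.1.2.3, with idasanutlin dose I and venetoclax dose V in mg:

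- logit p = α₁ + β₁ log(I/200); logit q = α₂ + β₂ log(V/400)
- π⁰ = p + q − pq
- π/(1−π) = π⁰/(1−π⁰) × exp(γ · I/200 · V/400)
- (α₁, log β₁): means −2.0 and 0.916, variances 1.665 and 0.002, covariance 0.037
- (α₂, log β₂): means −3.905 and 1.685, variances 1.47 and 0.003, covariance 0.0299
- log γ ~ N(0.4, 1.0), with 1.0 as the standard deviation

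Prior draws were weighted by the binomial likelihood, the product of π^x (1−π)^(n−x) over the doses tested. Runs with different seeds agreed within 0.001. Two assumed histories, written I/V:

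1. No DLT in 6 patients at 100/200, in 3 at 100/400 or in 3 at 200/200; last cohort at 200/400.
2. Minimum steps (50 mg idasanutlin, 100 mg venetoclax): no DLT in 6 at 100/200, in 3 at 100/300 or in 3 at 150/200; last cohort at 150/300.

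P(DLT rate >33%) at the next dose, which must be below 0.35:

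| Last cohort entered as | History 1, at 250/400 | History 2, at 200/300 |
|---|---|---|
| 1/3, case counted | 0.61, barred | 0.42, barred |
| 0/2, case dropped | 0.353, barred | 0.17, allowed |
| 0/3, DLT-free replacement | 0.29, allowed | 0.14, allowed |
| 1/4, case counted and a fourth patient added | 0.54, barred | 0.37, barred |

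With 3 rather than 6 patients at 100/200, the first three rows become 0.63, 0.36 and 0.30 for history 1, and 0.45, 0.18 and 0.15 for history 2.

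The effect also appears in a first cohort of three at 100/200. P at 150/200 is 0.48 with 1/3 (barred) and 0.12 with 0/3 (allowed).

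**The case against.** Four arguments go the other way.

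**Other routes stay open.** A DLT needs only one listed criterion, so failing the liver bullet does not make an event a non-DLT. An adverse event that prevents the next cycle altogether is naturally read as a delay of more than 14 days, and the discretionary clause fits an event that the protocol itself calls an indicator of severe liver injury. This is fair, and it makes a miscount possible rather than expected. But the first route depends on a reading the text does not state, and the second says only that such events may be counted.

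**The replacement rules are loosely joined.** The first rule in Section 3.1.2 concerns leaving the study, Section 4.6.2 concerns stopping treatment, and the missed-dose rule need not reach an event late in Cycle 2. That is correct. However, Section 4.6.2 alone is enough to replace the patient, and a patient who is not removed would stand in the data as DLT-free.

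**The illustration has limits.** It shows what any one uncounted DLT does, not something specific to the liver. In history 2, 150/400 stays allowed even after 1/3 (0.32, or 0.34 with 3 patients at 100/200), so escalation is not stopped altogether. The 0/2 row is not a state from which the next cohort can open, because Section 3.1.2.2 requires three patients to complete the window. Six patients at 100/200 pools two venetoclax schedules that Section 3.1.2.3 would by default model separately, and Study BH29812 data that may be added are left out. All of this stands. In history 1, the next step up for either drug is barred after 1/3 (250/400 at 0.61, 200/500 at 0.63), and 250/400 opens after a DLT-free replacement.

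**Dose decisions have other protection.** Clinical judgment overrides the model, adverse event and laboratory data are reviewed at each step, and Hy's Law cases are reported within 24 hours. This limits the harm but does not correct the count entered in the model.

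**Conclusion.** The concern holds. The contradiction is plain in the text, and a stated rule can give the escalation model a wrong DLT count. The gap is narrow: it needs a transaminase rise above 3 times baseline with jaundice, within two cycles, with no Grade 3 event other than a transaminase rise lasting under 7 days. It also needs the delay rule not to be read as covering permanent discontinuation and discretion not to be used. The documents give no rate for such cases, so the chance of a miscount cannot be stated.

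If it happens, the effect can decide a dose. In the assumed histories, replacing one uncounted patient by a DLT-free one moves 250/400 from 0.61 to 0.29, or 200/300 from 0.42 to 0.14, across the 0.35 limit. This should be fixed, because the fault lies in a safety rule and the correction is cheap.

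**What to change.** Replace the liver bullet in Section 3.1.2.1 with the Section 5.3.5.7 definition: treatment-emergent ALT or AST above 3 times baseline, together with either total bilirubin above 2 times ULN or clinical jaundice, when cholestasis and other causes of hyperbilirubinemia have been ruled out. State in Sections 3.1.2 and 4.6.2 that a Hy's Law discontinuation within the DLT window counts as a DLT and that the patient is not replaced as non-evaluable.

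Settle direct versus total bilirubin in the same edit. This is secondary, because its effect depends on ULNs that the documents do not give.

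The cost is protocol wording, a re-adjudication of liver events seen in Cycles 1 and 2, and an mCRM rerun if any are reclassified. No extra patients or visits are needed.
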